9.2. Setting

The three participating Sentinel Data Partners are discussed in Section 9.4. All Data Partners have access to electronic healthcare data (including insurance claims data and/or electronic health record data) that will be used to identify the study cohorts, outcomes, and covariate information.

^{*} The cohort study will identify HZ/su exposed and unexposed pregnancies for 5 years (July 1, 2021 to June 30, 2026). See Section 9.6.1 for a detailed description of the data collection period.

^{**} The descriptive analysis will identify exposed and unexposed pregnancies for 2 years (July 1, 2021 to June 30, 2023). See Section 9.6.1 for a detailed description of the data collection period.

Note: Annual surveillance report schedule is described in Section 9.6.1.2.

9.2.1. Study Population (Amended 15 August 2022)

The study population will include pregnancies among women who are diagnosed with IC conditions, with pregnancy start dates occurring during the period July 1, 2021 to June 30, 2026 (see Section 9.2.1.1 for description of the algorithm for estimation of pregnancy start dates). Singleton pregnancies among women who are diagnosed with IC conditions of systemic lupus erythematosus (SLE), multiple sclerosis (MS), rheumatoid arthritis (RA), IBD, PsO or psoriatic arthritis (PsA), solid organ transplant (SOT), stem cell transplant (SCT), hematologic malignancies (HM), solid tumors (ST), and human immunodeficiency virus (HIV) prior to and during early pregnancy will be identified from the DRN. Validated algorithms in the CBER BEST assessment report [Saunders-Hastings, 2021 will be used to identify IC conditions including solid organ transplant (SOT), stem cell transplant (SCT), hematological malignancy (HM), solid tumor (ST,) human immunodeficiency virus (HIV), as these are specific to each IC condition as well as valid and consistent with the typical approaches that are used in Sentinel, as shown in Appendix B: Validated Coding Algorithms for IC conditions. ICD-10-CM Codes for IC (Appendix A) and validated coding algorithms that have high positive predictive values (PPVs), i.e. >75%, will be used to identify study participants who are IC. These IC conditions were selected because they have the highest risk of HZ, with a high prevalence in pregnant women with IC conditions (see Table 1).

For autoimmune diseases (AIDs) (systemic lupus erythematosus [SLE], multiple sclerosis [MS], rheumatoid arthritis [RA], inflammatory bowel disease [IBD], psoriasis [PsO], and psoriatic arthritis [PsA]), coding algorithms from the literature that are AID-specific (Appendix B) will be used instead of the coding algorithms in the CBER BEST assessment report [Saunders-Hastings, 2021], as the algorithms that are presented in this report are not AID-specific.

Pregnancies will be included in the study if the following inclusion criteria are met:

- Participant who is pregnant with a pregnancy start date between July 1, 2021 and June 30, 2026. Live births are to be followed for 1 year.
- Participant is a female aged 18-49 years on the pregnancy start date.
- Participant meets study definition of SLE, MS, RA, IBD, PsO/PsA, SOT, SCT, HM, ST, or HIV (see Appendix A: ICD-10-CM Codes for IC and Appendix B: Validated Coding Algorithms for IC conditions). Codes for IC conditions will be identified in the health plan claims of the DRN during the period 273 days prior to the pregnancy start date through the first trimester (98 days after the pregnancy start date). Diagnoses recorded through the first trimester will be included to account for women who may not have frequent visits prior to pregnancy and may have a more complete assessment of medical conditions during the first prenatal care visit.
- Participant has at least 273 days of continuous health plan enrollment with medical and drug benefits prior to the start of pregnancy through the delivery date, with gaps of up to 45 days in coverage being permitted. The 273-day pre-pregnancy period through the first trimester (a period of 98 days after the pregnancy start date) was chosen to allow identification of potential confounders of interest (Section 9.3.3). In Sentinel projects, gaps of 45 days or less in health plan enrolment are

214420 (EPI-ZOSTER-039 VS US DB) Protocol Amendment 2 Final

typically considered administrative gaps (and not lapses in health plan coverage) and ignored.

Pregnancies will be excluded from the study if the following exclusion criterion is met:

- Participant was exposed to a medication(s) that presents a known increased risk for fetal malformations (see Appendix C: Teratogenic and Fetotoxic Medications)
- Participant delivered an infant identified as having a chromosomal or genetic anomaly (Appendix D: Diagnosis Codes for Chromosomal or Genetic Anomalies
- Ectopic pregnancies, molar pregnancies or induced abortions.
- Multigestation (e.g., twin) pregnancies.

For analyses evaluating infant outcomes (Primary Objective and Secondary Objective 1), the cohort will include pregnancies resulting in live births for which the mother is linked to an infant. Each Sentinel Data Partner will be responsible for linking mothers to infants using all available local data resources. Algorithms linking mothers to infants will vary across Data Partners, generally looking for equivalent health plan subscriber numbers, delivery dates and dates of birth, and shared names and addresses. Sentinel Data Partners are able to link approximately 74% of their infants to their mothers [Sentinel Initiative, 2018].

For analyses evaluating pregnancy outcomes (live birth, non-live births [stillbirth and spontaneous abortion]) and pregnancy complications (placental abruption, preeclampsia and eclampsia) (Secondary Objective 2), the cohort will include pregnancies resulting in a live birth and non-live birth (stillbirth), or spontaneous abortion.

For all analyses, the unit of analysis is a pregnancy episode.

9.2.1.1. Identification of Pregnancy Episodes and Gestational Age Assumptions

Sentinel investigators have developed publicly available tools to define medication exposures during pregnancy and comparatively assess pregnancy outcomes. These tools use a claims-based algorithm previously validated in the FDA-sponsored Medication Exposure in Pregnancy Risk Evaluation Program (MEPREP). The current study will use this algorithm to identify pregnancies ending in live births through identification of diagnosis and procedures codes listed in Appendix E: Live Birth Diagnosis and Procedure Codes. Because the date of the last menstrual period (LMP) is not available in the health plan data, the algorithm calculates the length of the pregnancy episode and the start of the pregnancy (i.e., LMP) using International Classification of Diseases, Tenth Revision, Clinical Modification (ICD-10-CM) codes indicative of weeks of gestation, as well as ICD-10-CM codes for preterm and post-term deliveries in the inpatient care setting (Appendix F: Codes to Identify Preterm and Post-term Birth). Specifically, the algorithm first prioritizes codes specifying completed weeks gestation, then non-specific preterm delivery codes (codes that indicate preterm birth but do not indicate a specific gestational age), and lastly non-specific post-term delivery codes (codes that indicate post-term birth but do not indicate a specific gestational age) identified within 7 days of

214420 (EPI-ZOSTER-039 VS US DB) Protocol Amendment 2 Final

the delivery encounter. ICD-10-CM incorporates diagnosis codes for gestational age in weekly increments. We assume the approximate mid-point of the specified gestational age (e.g., assumption of 263 days [37 weeks and 4 days] for ICD-10-CM code Z3A.37 [37 completed weeks gestation]). Gestational age assumptions are listed in Appendix F: Codes to Identify Preterm and Post-term Birth. If gestational age, preterm birth, or post-term delivery codes are not identified within 7 days of the delivery encounter, then the default assumption for gestational age for live birth deliveries is 273 days, based upon gestational lengths reported in published studies [Davidoff, 2006; Margulis, 2013]. The pregnancy start date (i.e., LMP) is then calculated by subtracting the gestational age from the date of the live birth delivery.

The LMP is widely accepted in electronic healthcare database safety studies as an estimate of the pregnancy start date and it is also in line with the European Medicines Agency (EMA) guidance. Numerous safety pregnancy studies have used LMP as an estimate of the pregnancy start date [Bateman, 2021; Hansen, 2016; Huybrechts, 2018; Kharbanda, 2021].

A published Sentinel study conducted within our Data Partners found \geq 90% agreement within 7 days between the claims data and medical charts for gestational age at stillbirth and 100% agreement within 30 days. Thus, misclassification of LMP based upon our algorithm to determine gestational age and LMP is expected to be minimal [Andrade, 2021].

Similar to the algorithm to determine live birth pregnancy episodes, ICD-10-CM and Current Procedural Terminology (CPT) codes will be used to identify non-live birth outcomes and calculate the length of the pregnancy episode, based upon published Sentinel [Andrade, 2021] and Vaccine Safety DataLink (VSD) studies [Naleway, 2021].

9.2.1.2. HZ/su-Exposed Group (Amended 15 August 2022)

Among the eligible cohort of live birth pregnancies linked to an infant (Primary Objective and Secondary Objective 1 cohort) and among the cohort of all eligible *live birth and non-live birth* pregnancies (Secondary Objective 2 cohort), women with IC conditions exposed to HZ/su during pregnancy will be identified. Exposure will be further categorized by stage of pregnancy: pre-pregnancy, first trimester, second trimester, and third trimester. The first trimester of pregnancy will be defined as 0 to < 14 weeks gestation, the second trimester as 14 to < 28 weeks, and the third trimester as 28 weeks through the end of the pregnancy.

A 30-day pre-pregnancy period (prior to LMP) will be included. There is no safety signal that would indicate that there is a risk pre-pregnancy. However, published vaccine safety studies have included varying pre-pregnancy periods [Kerr, 2020, Kharbanda, 2021, Panagiotakopoulos, 2020]. More recently published studies have included no pre-pregnancy or up to a 42-day pre-pregnancy period.

214420 (EPI-ZOSTER-039 VS US DB) Protocol Amendment 2 Final

9.2.1.3. Comparison (Unexposed) Group

Unexposed pregnancies among women with IC conditions who were not vaccinated with HZ/su (i.e., not receiving at least one dose of HZ/su during pregnancy) will be selected as a comparator with a 3:1 matching ratio to the pregnancies among women with IC conditions who were vaccinated with at least one dose of HZ/su (exposed pregnancies). This matching ratio of 1:3 was chosen because it is feasible, reduces bias and increases precision. Matching will be conducted separately for the eligible cohort of live birth pregnancies linked to an infant (Primary Objective and Secondary Objective 1 cohort) and among the cohort of all eligible live birth and non-live birth pregnancies (Secondary Objective 2 cohort).

We will monitor and evaluate the 1:3 matching plan during the feasibility assessment to see how the matching plan performs.

If the proposed matching plan performs poorly in practice (i.e., many unmatched HZ/su-exposed pregnancies would be excluded), we propose the following alternative matching plans:

- a. Exact match strategies:
 - Exactly match on DP, combined primary IC condition categories, maternal age (± 10 years), start date of the pregnancy period (± 120 days)
 - Exactly match on DP, combined primary IC condition categories, start date of the pregnancy period (± 120 days) and put age in the propensity score
- b. Propensity match strategies: Nearest neighbor matching with caliper width at 0.02, 0.03, 0.04, 0.05, 0.1 and 0.2 between propensities of the unexposed HZ/su and the HZ/su exposed

We will consider reducing the matching ratio of HZ/su-exposed to unexposed to 1:2 or 1:1 if the desired sample size cannot be achieved even with the relaxed matching plan. The corresponding sample size for 1:2 ratio will be 2436 (812 exposed and 1624 unexposed) and 2216 for 1:1 ratio (1108 exposed and 1108 unexposed) when maintaining the other assumptions (i.e., 90% power, 3% MCM prevalence, a type 1 error of 0.05 and a target risk ratio of 2.0).

[figure not shown]
The unexposed pregnancies must be pregnant/reached the week of gestational age of the exposed pregnancy (i.e., when exposure occurred) without an adverse event (i.e., spontaneous abortion or stillbirth).

Matching with a propensity score will minimize confounding bias due to differences between the HZ/su-exposed and comparator unexposed group. Propensity score matching is discussed below (Sections 9.3.3 and 9.7). Matching on DP, maternal age, and the start date of the pregnancy period, will control for DP differences in HZ/su use, age effects, and potential secular trends in HZ/su use and obstetric outcomes.

[figure not shown]
For each of these study samples, the unit of analysis is a pregnancy episode (Figure 2).

Figure 2 Study schema on study populations for the assessment of infant outcomes and pregnancy outcomes

Panel 1: Study Population for the Assessment of Infant Outcomes

Panel 2: Study Population for the Assessment of Pregnancy Outcomes

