It is plausible that the number of vaccine exposures during pregnancy may increase with the expansion of the HZ/su indication to adults aged 18 and older who are or will be at increased risk of HZ due to immunodeficiency or immunosuppression caused by known disease or therapy. Although currently unquantified, the number of pregnancy exposures is expected to be very low. This is likely only in the case of an unintended pregnancy because the vaccine is not recommended in this population, as per the Advisory Committee on Immunization Practice (ACIP) guidelines [Anderson, 2022].

Epidemiological evidence suggests that the risk of HZ in pregnant women with IC conditions is comparable to and sometimes exceeds the risk seen in the general female population [Gill, 2009; Nesheim, 2018]. Evidence also points at an increased prevalence of pregnancy among women with some IC conditions [Gill, 2009; Nabhan, 2010; Nesheim, 2018]. Table 1 describes the prevalence of IC conditions in pregnant women. Note that many of the estimates provided from published studies were obtained from diagnosis data reported in the inpatient setting (e.g., delivery hospitalization data); thus, estimates for some conditions (e.g., psoriasis (PsO), inflammatory bowel disease (IBD)) may be underestimated if the woman was not experiencing complications from the condition at the time of delivery admission.

214420 (EPI-ZOSTER-039 VS US DB) Protocol Amendment 2 Final

Table 1 Prevalence of IC conditions in pregnant women

IC condition	Prevalence (%) among pregnant women delivering an infant
Human immunodeficiency virus	0.03-0.13 [Ahmadzia, 2020; Arab, 2017; Nesheim, 2018]
Solid organ transplant	0.005 (liver) [Armenti, 2005] ^{1,2} 0.0005 (lung) [Shaner, 2012] ^{1,2}
Stem cell transplant	Not available
Systemic lupus erythematosus	0.08-0.14 [Chakravarty, 2006; Clowse, 2008 ² ; Mehta, 2019 ²]
Inflammatory bowel	0.09-0.13
disease	[Getahun, 2014; Nguyen, 2009]
Rheumatoid arthritis	0.04– 0.07 [Chakravarty, 2006; Kerr, 2020; Kharbanda, 2021; Kerr, 2020; Kishore, 2019]
Multiple sclerosis	0.03-0.13 [Fong, 2018; MacDonald, 2019]
Psoriasis/	0.03
Psoriatic arthritis	[Boddeda, 2018] ²
Solid tumors	Not available
Hematological malignancies	Not available

¹ As voluntarily reported to registry.

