9.5. Study size

All pregnancies among women who meet the study inclusion/exclusion criteria will be included in this study.

As the IC conditions included are heterogeneous and the number of MCMs for the primary outcome is likely small, the prevalence of each MCMs among each IC condition under study is not available. For sample size calculation for the cohort study, we employed the prevalence of overall MCMs (3%) in the general population [Holmes, 1976; Leppig, 1987; Marden, 1964; Van Regemorter, 1984] which might have a lower prevalence than among women with IC conditions. Therefore, the sample size calculated is relatively conservative. Assuming a 1:3 ratio of HZ/su-exposed to unexposed, a type 1 error of 0.05, and a target risk ratio of 2.0 for the primary safety outcome of MCMs, 711 live birth infants (live birth pregnancies linked to infant records) from the HZ/su-exposed group and 2133 live birth infants from the unexposed group will allow us to achieve 90% power.

The Power Analysis and Sample Size software (NCCS Statistical Software) was used in the sample size calculation.

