9.7.2.3. Sensitivity analyses

To ensure the robustness of the results, we will conduct sensitivity analyses to address the potential misclassification of the outcomes, potential unobserved confounders, and potential selection bias. When conducting the propensity score matching, we will use the nearest neighborhood matching with caliper width equal to 0.01 of the propensity score as the primary choice [Austin, 2010]. Other choices of caliper (i.e., 0.02 to 0.051) will also be compared to strike a desirable balance between the sample size and balances of baseline characteristics. Detailed sensitivity analyses and assessment of potential biases are documented in the SAP.

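### If 1:3 matching falls short, the fallback to a common 1:2 or 1:1 ratio raises the number of exposed pregnancies needed; variable-ratio matching serves better, and the fallback calipers need reconciling

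*Protocol*

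**What the plan says.** Section 9.5 sizes the cohort study at 1:3: "711 live birth infants (live birth pregnancies linked to infant records) from the HZ/su-exposed group and 2133 live birth infants from the unexposed group". The inputs are "Assuming a 1:3 ratio of HZ/su-exposed to unexposed, a type 1 error of 0.05, and a target risk ratio of 2.0", with a 3% malformation prevalence in the unexposed and 90% power.

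Section 9.2.1.3 sets out what happens if 1:3 matching loses many exposed pregnancies. The exact-match criteria are loosened first, together with the propensity caliper: "Nearest neighbor matching with caliper width at 0.02, 0.03, 0.04, 0.05, 0.1 and 0.2". If the target size is still out of reach, "We will consider reducing the matching ratio of HZ/su-exposed to unexposed to 1:2 or 1:1 if the desired sample size cannot be achieved". The protocol states the resulting sizes openly: 812 exposed and 1624 unexposed at 1:2, and 1108 and 1108 at 1:1, keeping "90% power, 3% MCM prevalence, a type 1 error of 0.05 and a target risk ratio of 2.0".

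Section 9.7.2.3 describes the "caliper width equal to 0.01 of the propensity score as the primary choice" and gives the other values to be compared as 0.02 to 0.051. It weighs sample size against baseline balance when choosing among them. Section 7 says that "the number of pregnancy exposures is expected to be very low".

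**The concern.** The exposed group limits this study; unexposed pregnancies in women with the same conditions should be far more plentiful. A lower common ratio economises on the plentiful group and asks for more of the scarce one. The step is taken when the desired sample size has not been reached, and its first effect is to raise the exposed part of that size. The protocol attaches no check that the cut keeps enough additional exposed pregnancies to pay for the comparators given up.

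The calipers raise a second question. They are absolute differences between predicted probabilities of vaccination. If vaccination in pregnancy is rare, most predicted probabilities lie close to zero, and a difference of 0.1 or 0.2 may exclude hardly any pair. Propensity matching is the main control for confounding in this study.

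**Working it through.** **1. The protocol's sizes.** Let p0 be the unexposed risk, p1 the exposed risk and k the comparators per exposed pregnancy, with p̄ = (p1 + k·p0)/(1 + k). The two-sided pooled-variance formula is

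n1 = [1.960·√{(1 + 1/k)·p̄(1 − p̄)} + 1.282·√{p1(1 − p1) + p0(1 − p0)/k}]² / (p1 − p0)².

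The base risk of 3% is from Section 9.5 ("we employed the prevalence of overall MCMs (3%) in the general population").

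- Risk ratio 2.0 (p1 = 0.06): 641, 733 and 1002 exposed at k = 3, 2 and 1.
- Odds ratio 2.0 (p1 = 0.06/1.03 = 0.05825): 711, 812 and 1109.

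The stated 711 and 812 are therefore reproduced, and 1108 to within one, by an odds ratio of 2.0 rather than the risk ratio the text names. Results are given on both bases; the direction is the same.

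**2. Rise in the exposed target.** 812/711 = 1.142 and 1108/711 = 1.558. On the risk-ratio basis, 733/641 = 1.144 and 1002/641 = 1.563.

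**3. Power if the number of exposed stays at 711.** Power = Φ{[√n1·(p1 − p0) − 1.960·√((1 + 1/k)·p̄(1 − p̄))] / √(p1(1 − p1) + p0(1 − p0)/k)}.

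For k = 3 and p1 = 0.06: (0.7999 − 0.4300)/0.2571 = 1.439, so 92.5%. For k = 1: (0.7999 − 0.5746)/0.2924 = 0.771, so 78.0%.

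| 711 exposed | 1:3 | 1:2 | 1:1 |
|---|---|---|---|
| Risk ratio 2.0 | 92.5% | 89.2% | 78.0% |
| Odds ratio 2.0 | 90.0% | 86.1% | 73.7% |

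**4. When a ratio cut pays.** It pays when retained exposed pregnancies rise by more than about 14% (1:2) or 56% (1:1). Starting below 711 the hurdle is higher: from 500 matched at 1:3 (odds ratio 2.0), equal power needs 578 at 1:2 (+16%) or 807 at 1:1 (+61%).

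**5. Fixed against variable ratio.** The protocol gives no distribution of available matches, so the mixes below are assumptions. Each totals 711 exposed, split by whether three, two or one comparators can be found. Fixed matching is taken to drop exposed pregnancies with too few comparators and to ignore surplus ones. Power is for a comparison stratified by set size with weights w = n1·n0/(n1 + n0) = n1·k/(k + 1):

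Power = Φ{[(p1 − p0)·Σw − 1.960·√(Σ w·p̄(1 − p̄))] / √(Σ w²·[p1(1 − p1)/n1 + p0(1 − p0)/n0])}.

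For 500/100/111, Σw is 500·3/4 = 375 at 1:3, 600·2/3 = 400 at 1:2, 711/2 = 355.5 at 1:1, and 375 + 66.7 + 55.5 = 497.2 with a variable ratio. Power at 3% against 6%:

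| Exposed with 3/2/1 matches | Fixed 1:3 | Fixed 1:2 | Fixed 1:1 | Variable 1 to 3 |
|---|---|---|---|---|
| 500/100/111 | 82.6% | 84.0% | 78.0% | 90.7% |
| 400/200/111 | 74.6% | 84.0% | 78.0% | 90.2% |
| 300/100/311 | 63.6% | 68.7% | 78.0% | 87.4% |
| 600/60/51 | 88.2% | 87.0% | 78.0% | 91.7% |

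At odds ratio 2.0 the first row is 78.9%, 80.3%, 73.7% and 87.9%. The variable ratio leads in every row because it keeps each exposed pregnancy that 1:1 keeps and each comparator that 1:3 keeps.

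**6. Calipers.** The protocol gives neither exposure prevalence nor a score distribution. With logit scores assumed normal (SD 0.5 to 1.0), a simulation gives the share of random exposed–unexposed pairs already inside each caliper:

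| Assumed exposure | 0.02 | 0.05 | 0.1 | 0.2 |
|---|---|---|---|---|
| 0.5% | 86–100% | 97–100% | 99.5–100% | 99.9–100% |
| 1% | 67–97% | 90–100% | 98–100% | 99.8–100% |
| 2% | 45–80% | 75–98% | 92–100% | 98.5–100% |
| 5% | 23–44% | 48–82% | 72–98% | 91–100% |

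For comparison, a caliper of 0.2 SD on the logit scale admits about 9 to 11% throughout.

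**The case against.** A reader might infer that the fallback defeats its own purpose. The documents do not support that. The relaxed plans are triggered by exposed pregnancies going unmatched, and where matches are the shortage a lower ratio can help: in the 400/200/111 mix, moving from 1:3 to 1:2 raises power from 74.6% to 84.0%. The larger exposed targets are disclosed, total size falls (2844, 2436, 2216), and the step is only to be considered. Nor does the protocol say that matching is strictly fixed-ratio; matching detail is left to the SAP, which is not available here. All of this stands, so the criticism is conditional.

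A reader might also infer that the relaxed calipers as a whole barely restrict, or that the balance safeguard is lost. Neither follows. For 0.02 to 0.05 the answer turns on a score distribution the protocol does not give. Nearest-neighbour selection still takes the closest comparator, the relaxed exact-match options keep data partner, condition category and start date, and Section 9.7.2.3 retains balance as a consideration. What remains is that 0.2 is loose at every exposure tried and 0.1 is loose up to about 2%.

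The value 0.051 may be 0.05 with a stray character. The two lists would still end at different values.

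Finally, a variable ratio is not free. Sections 9.7.2.1, 9.7.2.2 and 9.7.3 report prevalence by group, and unweighted pooled prevalences are not comparable when set sizes differ. That is a real cost, but manageable.

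**Conclusion.** The point holds in a conditional form. A lower common ratio raises the exposed requirement by 14% or 56% and, if matching is fixed-ratio, pays only when retention rises by more than about that. If exposed pregnancies as such are too few, it cannot help: at 711 exposed it costs about 3 to 4 percentage points of power at 1:2 and 14 to 16 at 1:1. Variable-ratio matching handles either cause of shortfall and had the highest power in every mix tried. The size of its advantage (90.7% against at most 84.0% in the first mix) rests on assumed match availability and on the fixed-ratio reading.

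On calipers, the mismatch between the two sections is plain from the text. The case for dropping 0.1 and 0.2 rests on assumed exposure and score spread, and is firm for 0.2 up to 5% exposure and for 0.1 up to about 2%. The change is worth making, because the protocol itself names the ratios and calipers; it does not show the primary 1:3 design to be wrong.

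**What to change.** - In Section 9.2.1.3, replace the 1:2 or 1:1 step with variable-ratio matching, 1 to 3 comparators per exposed pregnancy.
- Analyse by matched set, using the conditional logistic regression already named in Section 9.7.2.1 or a Mantel-Haenszel test stratified on set. Weight comparator prevalences by set.
- Give one fallback caliper list in Sections 9.2.1.3 and 9.7.2.3, without 0.1 and 0.2. A logit-scale caliper is an option, not a required correction.

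The cost is protocol wording, a matching-program option and weighted prevalence tables; no new data are needed. Tighter calipers may leave a few more exposed pregnancies unmatched in sparse cells, partly offset by keeping those with only one or two comparators.

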9.3. Variables

9.3.1. Exposure

Among the eligible cohort of live birth pregnancies linked to an infant (Primary Objective and Secondary Objective 1 cohort) and among the cohort of all eligible live birth and non-live birth pregnancies (Secondary Objective 2 cohort), HZ/su exposure will be defined as receipt of at least one dose of HZ/su during pregnancy. HZ/su vaccination will be identified by means of CPT code 90750 and National Drug Code (NDC) codes 58160-828-01, 58160-829-01, 58160-819-12, 58160-828-03, 58160-829-03, and 58160-823-11. We may include additional codes for identification of HZ/su exposure if relevant codes become available in the future. Pregnancies among women receiving at least one dose of HZ/su during pregnancy will be considered exposed. If a woman receives the vaccine before the start of pregnancy but does not receive the vaccine during the 30-day pre-pregnancy period or during pregnancy, she will not be considered exposed and would be considered for the comparator unexposed group. As described in Section 9.2.1.2, exposure will be further categorized by stages of pregnancy: pre-pregnancy, first trimester, second trimester, third trimester.

214420 (EPI-ZOSTER-039 VS US DB) Protocol Amendment 2 Final

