9.3.2.2. Pregnancy Complications and Outcomes (Secondary Objective 2)

The pregnancy outcomes to be evaluated include live birth, non-live birth (stillbirth, and spontaneous abortion). A stillbirth is defined as a spontaneous (non-deliberate) fetal death that occurs at or after 20 weeks' gestation but prior to delivery. A spontaneous abortion is defined as a spontaneous (non-deliberate) embryonic or fetal death that occurs prior to 20 weeks' gestation. Placental abruption (ICD-10-CM O45.X) will be identified by searching the mother's claims from 20 weeks gestation through the date of delivery. Preeclampsia and eclampsia (ICD-10-CM O11.X, O14.X, O15.X) will be identified by searching the mother's claims from 20 weeks gestation through the date of delivery. A prior study conducted at one U.S. hospital found that the sensitivity of preeclampsia and eclampsia inpatient codes are generally low, however the PPV and specificity were high [Labgold, 2021].

Pregnancy outcomes will be identified in claims data through diagnosis and procedure codes (Appendix E. Live Birth Diagnosis and Procedure Codes and Appendix H. Spontaneous Abortion and Stillbirth Codes). Pregnancy episodes resulting in a live birth will be identified using validated algorithms (see Section 9.2.1.1) that have been used in Sentinel and non-Sentinel projects [Andrade, 2012; Andrade, 2016; Johnson, 2013; Sentinel Initiative, 2018]. Pregnancy episodes ending in a non-live birth pregnancy outcome will be identified using algorithms developed through Sentinel and non-Sentinel (e.g., VSD) projects [Andrade, 2021; Naleway, 2021].

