Pregnancy outcomes will be compared between eligible pregnancies among women with IC conditions who were vaccinated with HZ/su during pregnancy and those who were not vaccinated with HZ/su during pregnancy. Univariate and multivariable statistical analyses will be performed as stated in the primary objective and secondary objective 1 (Section 9.7.2.1) for all outcomes. The prevalence of the pregnancy outcomes (live birth, stillbirth, and spontaneous abortion) and pregnancy complications (placental abruption, preeclampsia and eclampsia) and their 95% CIs will be calculated between the two groups of women. All analyses will be stratified by stage of pregnancy (pre-pregnancy, first trimester, second trimester, third trimester).

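### Comparators are aligned to the gestational week of the matched dose, not the day, which leaves a small avoidable bias in the spontaneous-abortion contrast

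*Protocol*

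**What the plan says.** - **Comparator rule (Section 9.2.1.3).** "The unexposed pregnancies must be pregnant/reached the week of gestational age of the exposed pregnancy (i.e., when exposure occurred) without an adverse event". The adverse events meant are spontaneous abortion and stillbirth. The anchor is a gestational week; no index day is named.
- **Exposure (Section 9.3.1).** "HZ/su exposure will be defined as receipt of at least one dose of HZ/su during pregnancy". A pregnancy therefore enters the exposed group only if it was ongoing when the dose was given. The last exposure window is open to the end: "the third trimester as 28 weeks through the end of the pregnancy" (Section 9.2.1.2).
- **Outcome (Section 9.3.2.2).** Spontaneous abortion is an "embryonic or fetal death that occurs prior to 20 weeks" of gestation.
- **Contrast (Section 9.7.2.2).** "Pregnancy outcomes will be compared between eligible pregnancies among women with IC conditions who were vaccinated with HZ/su during pregnancy" and those not vaccinated, stratified by stage of pregnancy. The descriptive fallback (Section 9.7.3) uses the same kind of matched comparators.
- **Separate cohorts (Section 9.2.1.3).** "Matching will be conducted separately for the eligible cohort of live birth pregnancies linked to an infant", and again for the cohort of all eligible pregnancies. Only the latter carries spontaneous abortion.
- **Dating (Section 9.2.1.1).** Gestational age comes from weekly codes: "We assume the approximate mid-point of the specified gestational age". The validation cited is for stillbirth, with at least 90% "agreement within 7 days between the claims data and medical charts for gestational age at stillbirth and 100% agreement within 30 days".

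**The concern.** In a comparison of pregnancy loss, both groups should start being at risk at the same gestational point. An exposed pregnancy dosed on, say, day 5 of a week has survived to day 5. A comparator that only has to have reached that week may be lost on days 0 to 4 and still qualify, and that loss counts as an event. The same loss in a would-be exposed pregnancy would have prevented vaccination, so it can never appear on the exposed side.

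If the sentence is programmed the other way, as no event during the whole of that week, the imbalance reverses: losses after the dose but within the week count only in the exposed.

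Spontaneous abortion is a Secondary Objective 2 safety outcome. Under the literal reading the error points towards concealing harm; under the whole-week reading it points towards a false signal. A programmer could reasonably implement either.

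**Working it through.** **Length of the mismatch.** With the dose day uniform within its week, the extra comparator time under the literal rule is (0+1+2+3+4+5+6)/7 = 3 days on average and 6 at most. Losses in earlier weeks are excluded from both groups.

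**Inputs from the protocol.** Spontaneous abortion ends at 20 weeks (day 140). The first trimester is weeks 0 to under 14 (days 0-97). There is no stated figure to reproduce: the protocol gives no rate, sample size or power for spontaneous abortion.

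**Inputs assumed.** No vaccine effect; total loss risk 10%, 15% or 20%; losses on days 35-139 with a bell-shaped daily hazard centred at day 60 (SD 18 days); dose days uniform over the window.

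**Formulas.** Let S(t) be the probability of still being pregnant at the start of day t. For a dose on day d:
- exposed risk = 1 - S(140)/S(d)
- comparator risk, literal rule = 1 - S(140)/S(7 x floor(d/7))
- comparator risk, whole-week reading = 1 - S(140)/S(7 x floor(d/7) + 7)

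Each is averaged over d, and the risk ratio (RR) is the ratio of the averages. With day-level alignment the first two expressions coincide, so RR = 1.

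**Results at 15% total risk.**

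| Dose window | Exposed | Comparator, literal | RR | Comparator, whole week | RR |
|---|---|---|---|---|---|
| Days 0-34 | 0.1500 | 0.1500 | 1.00 | 0.1500 | 1.00 |
| Days 0-55 | 0.1426 | 0.1451 | 0.98 | 0.1389 | 1.03 |
| Days 0-97 (first trimester) | 0.0986 | 0.1031 | 0.96 | 0.0926 | 1.06 |
| Days 35-97 (weeks 5-13) | 0.0700 | 0.0771 | 0.91 | 0.0608 | 1.15 |

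At 10% and 20% total risk the ratios are almost unchanged. For weeks 5-13 the literal-rule risk difference is about 0.5 to 0.9 percentage points across that range.

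**Mid-week dating of losses.** If losses are all dated at week plus 4 days (the Section 9.2.1.1 convention, 37 x 7 + 4 = 263), doses on days 0-4 precede that week's losses and doses on days 5-6 do not. Exposed risk for weeks 5-13 is then 5/7 x 0.0771 + 2/7 x 0.0608 = 0.0724. The RR is 0.0724/0.0771 = 0.94 (literal) or 0.0724/0.0608 = 1.19 (whole week). Coarse dating changes the size but does not cancel the effect.

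**Other hazard shapes, literal rule.** With losses over weeks 4-19 and a weekly hazard that is flat or falls 10% or 20% per week, at 10-20% total risk, the RR is 0.91 to 0.97 for doses in weeks 4-13 (risk difference about 0.3 to 0.8 points) and 0.95 to 0.98 for weeks 0-13. For a single dose in week 16 it is about 0.86 to 0.90, but few losses remain: the difference at 15% total risk is only 0.10 to 0.42 points.

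**The case against.** A reader might infer that losses before vaccination in general count only in comparators, that is, that immortal time is uncorrected. The protocol does not support that. The quoted sentence exists to remove it and does so for every week before the dose week. The difference is large: under the same alternative hazard shapes, with no alignment at all, a week-10 dose would give an RR of about 0.25 to 0.65.

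A reader might also infer that the plan makes a harmless vaccine look protective. That follows from one of three readings. The sentence requires the comparator to be pregnant and ties this to when exposure occurred, which can fairly be read as still pregnant at the time of the dose. That reading is sound. It stands as a reason to call this an ambiguity rather than an established bias.

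The weeks 5-13 figure also leaves out the earliest doses. Section 7 expects vaccination before women know they are pregnant, and for doses before day 35 the model bias is nil. The protocol gives no distribution of dose weeks, so neither end of the range can be preferred.

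The bias is small against attainable precision. Taking 9.9% risk in both groups and, for illustration, the malformation sample of 711 exposed and 2133 unexposed, the 95% interval around RR 1 is exp(±1.96 x sqrt(0.901/(711 x 0.099) + 0.901/(2133 x 0.099))), about 0.77 to 1.29. With 237 exposed at 1:3 it is about 0.64 to 1.56. In the fallback no statistical comparison is made, and the comparator prevalence would shift by only 10.31% - 9.86% = 0.45 points over the first trimester.

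Finally, matching detail is deferred to the SAP, which is not shown, and Figure 2 could not be read. The SAP may name an index day. The eligibility rule, however, is stated in the protocol, and its wording permits results on opposite sides of 1.

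The argument that weekly dating makes the point moot does not stand. Whether a dose precedes the end of pregnancy is settled by two calendar dates. If dating error is alike in both groups, day-level alignment restores a common start on the measured scale.

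**Conclusion.** The point holds as a minor one. The rule controls losses in earlier weeks but leaves up to 6 days (mean 3) inside the dose week unaligned, and the sentence can be programmed three ways, one of them sound. Under no vaccine effect and the assumed hazards, the spontaneous-abortion risk ratio over the first trimester is about 0.96 on the literal rule and 1.06 on the whole-week reading. It is 1.00 for doses before week 5, and about 0.91 and 1.15 respectively for weeks 5-13.

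All loss rates, hazard shapes and dose-day distributions are assumptions. Only the spontaneous-abortion contrast of Secondary Objective 2 is materially affected. Malformations and the other infant outcomes sit in the separately matched live-birth cohort; doses before the last menstrual period (LMP) carry no bias; the effect on stillbirth is negligible.

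**What to change.** In Section 9.2.1.3, replace the reference to the gestational week with the gestational day of the matched dose, defined as dose date minus estimated LMP. Then state that:
- the comparator must still be pregnant at the end of that same gestational day, with no spontaneous abortion, stillbirth or delivery;
- a dose counts as in-pregnancy exposure only if dated before the recorded end of pregnancy;
- outcomes count from the next day in both groups, and from LMP in both groups for doses in the pre-pregnancy window.

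If the SAP already names an index day, bring the protocol sentence into line with it.

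Cost: one sentence or two and a small change to the matching program. No new data are needed, and a few comparators will be replaced. The limitation is that a day-level gestational age is nominal, because LMP is estimated from weekly codes. The repair therefore relies on that error being similar in the two groups.
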